4.2 SCIENTIFIC RATIONALE FOR STUDY DESIGN

This study involves a direct-to-participant approach that minimizes participant burden and accelerates translation of study findings into daily life settings. This study designs bypasses the traditional settings within healthcare environments, and instead brings study procedures to the participants' homes. A direct-to-participant approach minimizes risks by leveraging the public health intervention community engagement, recruitment, and intervention dissemination efforts, and maximizes rewards by selectively complementing study data with participant specific information on behaviors and clinical outcomes associated with frequent at-home testing.

The objective of the study is to gather participant level information about social behaviors in response to at-home test results during the SARS-CoV-2 pandemic. Therefore, a direct-to-participant design, which maximally integrates assessments into participant's lifestyle was deemed best suited to provide accurate representation of behaviors.

There are certain limitations to this study design. A slow enrollment is the greatest challenge to any prospective cohort study. By nesting the sub-study within the public health intervention, the sub-study leverages the multimodal community engagement and kit dissemination strategies of the public health intervention. Non-compliance with study procedures is a risk for community based and direct-to-participant studies, where traditional health care visits are not available to perform procedures or reinforce compliance. Participation will be facilitated by creating two participation pathways, app and call center enabled.

As a result of these efforts, the goal is to establish a systematic approach combining community engagement and at-home testing to decrease transmission of SARS-CoV-2 as well as inform public health interventions for future pandemics.

4.3 JUSTIFICATION FOR DOSE

There is no study specified administration of a test product. The SARS-CoV-2 test is being self-administered as part of the public health intervention, and is not part of this sub-study protocol.

4.4 END OF STUDY DEFINITION

A participant is considered to have completed the study if he or she has completed the active testing period (at-home testing 3 times a week for 4 weeks) along with the questionnaires/surveys during those 4 weeks. Questionnaires/surveys will continue to be offered during the follow-up period (up to 17 weeks). Any amount of testing data and survey responses completed will be acceptable and analyzed.

5 STUDY POPULATION

5.1 INCLUSION CRITERIA

In order to be eligible to participate in this study, an individual must meet all of the following criteria:

1. Self-reported primary residence within the pre-identified communities
2. Age > 8 years at enrollment
3. Provision of signed and dated informed consent form

5.2 EXCLUSION CRITERIA

There are no exclusion criteria for this study, if all above inclusion criteria are met.

5.3 LIFESTYLE CONSIDERATIONS

Not applicable

5.4 SCREEN FAILURES

Screen failures are defined as participants who consent to participate in the sub-study but are not subsequently entered in the study because they do not meet the inclusion criteria for participation or decide not to participate at anytime

5.5 STRATEGIES FOR RECRUITMENT AND RETENTION

Participants for this sub-study will be recruited within the communities participating in the larger public health intervention. Recruitment strategies include marketing with public health messaging in collaboration with local health departments, media and targeted social media outreach for awareness and education, as well as other strategies that would be tailored to the different distribution scenarios. Participants may be compensated up to \$50 for completion of all surveys. The sample size is up to 300,000 for the sub-study. The test kits distributed as part of the larger study will contain information about the sub-study and how-to consent using either a mobile device based application (e-consent) accessible free of charge to participants or via phone consenting (verbal consent). All participants who consent to the sub-study could be re-contacted for future research opportunities. An option to opt-out of re-contacting will be provided in the consent.

6 STUDY INTERVENTION

6.1 STUDY INTERVENTION(S) ADMINISTRATION

6.1.1 STUDY INTERVENTION DESCRIPTION

The smartphone app used in this study, MyDataHelps, is an NIH funded app that uses secure file transfer protocols and can administer consent forms, surveys, and capture multimedia information.

6.1.2 DOSING AND ADMINISTRATION

Not Applicable

6.2 PREPARATION/HANDLING/STORAGE/ACCOUNTABILITY

Not Applicable

6.2.1 ACQUISITION AND ACCOUNTABILITY

Not Applicable

6.2.2 FORMULATION, APPEARANCE, PACKAGING, AND LABELING NOT APPLICABLE

Not Applicable

6.2.3 PRODUCT STORAGE AND STABILITY

Not Applicable

6.3 MEASURES TO MINIMIZE BIAS: RANDOMIZATION AND BLINDING

This study will be conducted as a non-randomized cohort sub-study design to assess the individual social behavior during a community level at-home testing program. Eligible communities receiving will be selected per criteria in the public health intervention.

6.4 STUDY INTERVENTION COMPLIANCE

Push notifications will be programmed in the app along with text messaging to promote adherence to the at-home testing schedule as well as the survey and questionnaire schedule as part of the public health intervention. The app also includes a personal tracker of participant test history. Phone call reminders will be provided for participants who choose not to use the app. Deviations to the public health intervention will not be tracked.

6.5 CONCOMITANT THERAPY

Not applicable

6.5.1 RESCUE MEDICINE

Not applicable

7 STUDY INTERVENTION DISCONTINUATION AND PARTICIPANT DISCONTINUATION/WITHDRAWAL

7.1 DISCONTINUATION OF STUDY INTERVENTION

No study intervention-not applicable

7.2 PARTICIPANT DISCONTINUATION/WITHDRAWAL FROM THE STUDY

Participants are free to withdraw from participation in the study at any time. The reason for participant discontinuation or withdrawal from the study will be collected on the app or through phone call via call center. Participants who provide consent, and subsequently withdraw, will not be replaced.

7.3 LOST TO FOLLOW-UP

A participant will be considered lost to follow-up if he or she fails to complete the at-home testing and scheduled questionnaires/surveys and is unable to be contacted by the call center.

The DCRI call center will attempt to contact the participant and counsel the participant on the importance of maintaining the assigned study schedule and ascertain if the participant wishes to and/or should continue in the study. Should the participant continue to be unreachable, he or she will be considered to have withdrawn from the study with a primary reason of lost to follow-up.

8 STUDY ASSESSMENTS AND PROCEDURES

8.1 EFFICACY ASSESSMENTS

The questionnaires/surveys will assess patient-report outcomes related to social behaviors, healthcare utilization, knowledge of SARS CoV-2 prevention approaches, and the feasibility of at-home self-administered testing. Adherence to the at-home testing and questionnaire/survey schedule will also be assessed.

8.2 SAFETY AND OTHER ASSESSMENTS

The healthcare utilization questionnaire will be routinely administered during the treatment and follow-up phase, and it will ask about any emergency department visits, hospitalizations, and ICU admission related to SARS COV-2 evaluation or treatment.

8.3 ADVERSE EVENTS AND SERIOUS ADVERSE EVENTS

8.3.1 DEFINITION OF ADVERSE EVENTS (AE)

Not applicable

8.3.2 DEFINITION OF SERIOUS ADVERSE EVENTS (SAE)

Not applicable

8.3.3 CLASSIFICATION OF AN ADVERSE EVENT

8.3.3.1 SEVERITY OF EVENT

Not applicable

8.3.4 TIME PERIOD AND FREQUENCY FOR EVENT ASSESSMENT AND FOLLOW-UP

Not applicable

8.3.5 ADVERSE EVENT AND SERIOUS ADVERSE EVENT REPORTING

Not applicable

9 STATISTICAL CONSIDERATIONS

Additional details of the planned statistical analyses will be provided in a separate statistical analysis plan.

9.1 STATISTICAL HYPOTHESES

The proposed analysis is primarily descriptive rather than inferential, as it designed to provide a general assessment of participant level behaviors in the context of a community testing intervention. An exploratory hypothesize is that positive at-home SARS-CoV-2 antigen test results will lead to altered self-reported social interactions and altered health behaviors compared to negative test results.

9.2 SAMPLE SIZE DETERMINATION

A formal power calculation is not performed for this observational cohort study. However, a sample size in the ranges of 1000 to 10,000 participants would be sufficient to estimate positive test incidence and prevalence, describe behavioral changes associated with test results, and conduct multivariable modeling to inform understanding of the causal chain between frequent testing and community burden of disease. To illustrate this, suppose the proportion of participants who adhere to social distancing is 50%. In that case, a sample size of 5,000 participants will be sufficient at a confidence level of 95% to estimate the prevalence with a margin of error of 1.5%. Additional examples of estimate precision at varying sample sizes are provided below. Overall, even with a sample size of 1000 participants and for an endpoint with a 50% proportion, there will be a 95% chance that the real value of this proportion is within 3.1% of the observed value.

Sample Size N=	Point estimate of proportion	Margin of error
10,000	1%	0.19%
10,000	10%	0.58%
10,000	50%	0.96%
10,000	80%	0.77%
5000	1%	0.27%
5000	10%	0.82%
5000	50%	1.37%
5000	80%	1.10%
1000	1%	0.62%
1000	10%	1.86%
1000	50%	3.09%
1000	80%	2.48%

9.3 POPULATIONS FOR ANALYSES

The following populations are also defined:

Population	Description
Evaluable Population- Per protocol (PP)	Per protocol population will be those that report adhering to the following: 
 1. Self-administer the at-home test three times a week for 4 weeks 2. Complete questionnaires/surveys during the 4 week testing period
Modified per-protocol	Will include any participant who performed at least one at-home test
Second modified per-protocol	Will include any participant who completed at least one survey

All analyses will be conducted in the PP. A subset of analyses will be repeated in the modified PP populations as applicable.

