1.2 SCHEMA

1.3 SCHEDULE OF ACTIVITIES (SOA)

Study Period/Phase:	Screening & Enrollment Phase	Sub-study Questionnaires/Surveys							Comments & Notes	
		Testing Phase (Public Health Intervention)*				Follow-Up Phase				
Week:	Weeks-4 to 0	Baseline	Week 1	Week 2	Week 3	Week 4	Week 5	Week 13	Week 21	
Informed Consent and Assent when applicable		X								e-Consent via app or verbal consent via call center
Create mobile app account		X								For participants using the mobile app
Contact Information		X								
Socio-Demographic Data		X								
Medical History		X								
Anthropometrics – Weight		X				X				
Anthropometrics – Height		X								
Questionnaires										Questionnaires can be completed during the week after each test (regardless of the result).
• Social interactions		X	X		X		X	X	X	
• Behaviors										
• Symptoms										
• Healthcare utilization										
• Beliefs		X	X				X		X	
• Knowledge of prevention approaches							X		X	
• Feasibility of at-home testing							X			
Testing Adherence/Compliance reminders			X	X	X	X	X	X	X	

*The public health intervention (3 times a week at-home testing) does not require consent. Consent is only required for this sub-study which involves the questionnaires/surveys that are administered during the testing phase and follow-up phase.

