9.4.2 ANALYSIS OF THE PRIMARY EFFICACY ENDPOINT(S)

Point estimates with 95% confidence intervals will be reported. The analysis will be done for applicable study populations as described above, and stratified by participant demographics of interest (e.g., age, gender). There will be a comparison of the proportion of participants that report adhering to social distancing guidelines after positive vs. negative test result.

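### Section 9.3 puts all analyses in a per-protocol set fixed in or after the weeks when test results arise, which leaves the estimates open to selection bias and conflicts with Section 4.4

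*Combined protocol and SAP*

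**What the plan says.** Section 9.3 defines three sets. PP is made up of people who report both the thrice-weekly, 4-week testing schedule and completion of the surveys in that period. The two wider sets need only one test, or only one survey. The assignment rule is: "All analyses will be conducted in the PP. A subset of analyses will be repeated in the modified PP populations as applicable". No minimum share of tests or surveys is given, and there is no exemption for someone who stops testing after a positive result or falls ill. The analyses to be repeated are not listed.

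Other sections bear on this:

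- Section 9.4.2, on the primary endpoint, refers back without choosing a set: "The analysis will be done for applicable study populations as described above".
- Section 4.4 defines completion much as PP does, but ends: "Any amount of testing data and survey responses completed will be acceptable and analyzed".
- Section 3 attaches entire-cohort wording to the primary, secondary and most exploratory endpoints. Section 9.4.3 (behaviour, knowledge, prevalence) and Section 9.4.4 (feasibility, vaccine attitudes) repeat it. Section 9.3 defines no all-enrolled set.
- Section 9.4.1 plans the positive-versus-negative comparison as a test of proportions clustered by participant.
- Section 9 defers detail: "Additional details of the planned statistical analyses will be provided in a separate statistical analysis plan".

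**The concern.** In the primary comparison the exposure is the test result. It arises inside the 4 weeks that a participant must complete to enter PP, so membership is settled in or after the weeks of exposure. It may depend on the result, on illness, or on the behaviour being measured. An estimate restricted to PP then describes self-reported full compliers, who may differ from the people the study set out to describe.

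Three kinds of result are exposed:

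- **Prevalence**, if people who test positive complete the schedule at a different rate from the rest.
- **Utilisation**, if people with a COVID-related visit in the testing weeks do so.
- **The primary comparison**, if completion is related to distancing.

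Read literally, the rule also drops people who answered the week 5, 13 or 21 surveys but did not report every scheduled test. Under Section 1.3, knowledge is asked only at weeks 5 and 21, and "Feasibility of at-home testing" only at week 5, all after the testing weeks.

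Section 9.2 says that 1,000 to 10,000 participants "would be sufficient to estimate positive test incidence and prevalence, describe behavioral changes associated with test results". Its margins cover sampling error only. Recruiting more people, up to the stated 300,000, would not remove selection of this kind.

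**Working it through.** **Inputs.** From the documents: 3 tests a week for 4 weeks, so 12 tests; 95% confidence; margins of 0.58% (10,000 people, proportion 10%) and 0.19% (10,000, 1%) in Section 9.2; up to 300,000 participants. Assumed, because the documents give none: true prevalence of 10% or 1% (both are rows of the 9.2 table); r, the PP completion of positives relative to negatives; q, the chance that each test is done; k, the PP completion of distancers relative to non-distancers.

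**1. The plan's margins.** 1.96 × √(0.10 × 0.90 / 10,000) = 0.588%. A finite-population factor √((300,000 − 10,000)/299,999) gives 0.578%, the stated 0.58%. At 1% the same steps give 0.195% and then 0.192%, the stated 0.19%. The correction is inferred, but with it all 12 table entries reproduce. The table is not in dispute.

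**2. Prevalence seen in PP** = p·r / (p·r + 1 − p).

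| r | true 10% reads | true 1% reads |
|---|---|---|
| 0.75 | 7.69% | 0.75% |
| 1.25 | 12.20% | 1.25% |

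**3. The r at which the shift equals the margin, with 10,000 in PP.** Put a = p − m or p + m, where m is the margin; then r = a(1 − p) / (p(1 − a)).

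- At 10%, a = 9.42% gives 0.936 and a = 10.58% gives 1.065.
- At 1%, a = 0.81% gives 0.81 and a = 1.19% gives 1.19.

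**4. If instead 10,000 are enrolled.** With independent tests, the number meeting the testing criterion is 10,000 × q^12: 2,824 at q = 0.90 and 5,404 at q = 0.95. The margin is 1.96 × √(p(1 − p)/n).

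| true prevalence | margin (n = 2,824; 5,404) | shift at r = 0.75 | shift ÷ margin |
|---|---|---|---|
| 10% | 1.106%; 0.800% | 2.31 points | 2.1; 2.9 |
| 1% | 0.367%; 0.265% | 0.25 points | 0.7; 0.9 |

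**5. Utilisation** follows the formula in step 2, with r now comparing people with and without a visit. A true 2% reads 1.01% at r = 0.5 and 2.97% at r = 1.5.

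**6. Primary comparison, as two separate groups of people.** Distancing seen in PP = d·k / (d·k + 1 − d), where d is the true share who distance.

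- True 80% vs 50%, k = 2 in both groups: 88.9% vs 66.7%. The difference falls from 30 to 22.2 points; the odds ratio stays 4.0.
- True 50% vs 50%, same k in both groups: the difference stays 0.
- True 50% vs 50%, k = 1.25 after a positive only: 55.6% vs 50.0%, a spurious +5.6 points. With k = 0.8 after a positive only: 44.4% vs 50.0%, or −5.6 points.

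So a difference between truly equal groups needs completion to depend on distancing differently after a positive than after a negative result. These figures show the mechanism only. Under Section 9.4.1 one person can contribute results of both kinds, so they are not effects on the planned clustered estimator.

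**The case against.** The case for leaving the plan alone has real content.

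- **The aim is mainly descriptive, with an exploratory hypothesis (Section 9.1).** That lowers the stakes for testing. It does not protect a descriptive prevalence or adherence figure, which selection affects directly.
- **A separate SAP is promised and was not among the documents.** It may settle the matter, but deferring additional detail does not cancel an explicit rule for all analyses.
- **The wider sets already exist.** This is true, so the gap is which set leads and which analyses are repeated.
- **Entire-cohort wording may mean only unstratified.** This stands as a possible reading. On it, the firm conflict is with the last sentence of Section 4.4 alone.
- **PP may be closer to the intended regimen.** Section 2.1 describes testing regardless of symptoms or exposure. The at-least-one-test set admits people who test only when ill or exposed, which may raise prevalence. This stands: the documents do not show that the wider sets are less biased for every endpoint.
- **Missed tests are not tracked (Sections 6.4 and 10.1.10).** This stands in part. Section 8.1 says "Adherence to the at-home testing and questionnaire/survey schedule will also be assessed", but a missed test and an unreported one may look the same.

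A reader might infer that people stop testing after a positive result, so that PP removes them and understates prevalence. The documents do not support that. Testing "is being self-administered as part of the public health intervention, and is not part of this sub-study protocol" (Section 4.3), and the intervention's instructions were not supplied. A reader might also infer that PP would be too small. Precision is not the concern: even 2,824 lies within the range that Section 9.2 calls sufficient.

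**Conclusion.** The point holds as a finding about a stated rule and its conflict with other text. Section 9.3 conditions every analysis on self-reported full completion, gives no tolerance, and leaves the repeats unnamed. Confidence is high that the rule exists and that it conflicts with Section 4.4. Confidence is moderate that material bias would follow.

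Neither size nor direction can be fixed from the documents. With 10,000 in PP, the prevalence shift exceeds the stated margin once r leaves about 0.94 to 1.06 at a true 10%, or 0.81 to 1.19 at a true 1%. In smaller PP sets, whether the shift matters depends strongly on true prevalence. All of this rests on assumed completion rates and, for the PP sizes, on tests being independent. It would be too strong to say that the primary comparison will be spurious: that needs a differential pattern of completion which the documents neither show nor exclude. This is a cheap improvement, not a threat to the study's viability.

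**What to change.** Replace the all-analyses rule in Section 9.3 with a lead set for each endpoint:

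1. **Primary and behaviour:** participants with at least one reported test result and a later survey that holds the outcome.
2. **Prevalence:** the existing at-least-one-test set, reported per test or per week, stating how tests after a first positive are counted. Show PP prevalence beside it.
3. **Utilisation, knowledge and feasibility:** members of the existing at-least-one-survey set who answered a survey that collects the outcome.

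Keep PP as a named sensitivity analysis for each endpoint. Report PP completion by test result, from reported data, so that readers can judge r. Reconcile Section 9.3 with Sections 3, 4.4, 9.4.3 and 9.4.4, saying what entire-cohort means; if PP is to lead, give the reason in the SAP.

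The cost is protocol and SAP wording; the analyses use data already reported under the plan. The downsides should be stated:

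- Some selection on survey response remains in sets 1 and 3.
- Set 2 admits people who test only when ill or exposed.
- Because deviations are not tracked, completion by test result is partly a reporting rate.
- Unequal testing makes an ever-positive proportion unsafe in set 2. If 5% would be positive over 12 equally risky tests, the per-test risk is h = 1 − 0.95^(1/12). Then 3 tests give 1 − (1 − h)^3 = 1.3% and 6 tests give 1 − (1 − h)^6 = 2.5%, hence the per-test or per-week basis.

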9.4 STATISTICAL ANALYSES

9.4.1 GENERAL APPROACH

The approach to analysis will be primarily descriptive. Demographics, questionnaire data, and testing results will be reviewed and summarized using graphical techniques and summary statistics. Where applicable, exact method confidence intervals will be computed around point estimates. Trends over time will be evaluated graphically. The proportion of participants adhering to social distancing guidelines after a positive vs. negative test result will be compared using tests of proportion clustered by participants with various levels of intra-participant correlation. Stratified analyses by test or week number will also be performed. We will explore the associations between positive test results and critical behavioral measures using mixed modeling techniques to account for the participant and

household correlations. Analyses will be conducted using SAS (SAS Institute, Cary NC) and R with R Studio (R-project).

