4 STUDY DESIGN

4.1 OVERALL DESIGN

This is an observational, direct-to-participant, nested cohort, sub-study embedded within a public health intervention that distributes at-home, self-administered, SARS-CoV-2 antigen testing kits. Adults and children over 8 years of age living within the pre-identified communities will be included. This sub-study focuses on gathering participant-level data to evaluate behavioral determinants of home testing and socio-behavioral mechanisms of SARS-CoV-2 community transmission.

The smartphone application developed by CareEvolution, called MyDataHelps, will be used for this study, and it is free of charge on Apple or Android devices³. As part of the public health intervention, households will receive test kits and included in them will be information about the app and a QR code to facilitate access. Only after the participants have received information about the public health intervention and received the testing kits, will they be offered the option to participate in this sub-study. Once registered, if the participant wants to be a part of the sub-study, eligibility criteria will be verified and e-consent will be obtained through the app. The smartphone app includes instructions to administer at-home tests, for all participants in the public health intervention. Push notifications will be programmed with messaging to promote adherence including personalization, context, and timing for all participants in the public health intervention. Additionally, participants will have an option to opt-in to reminders for testing 3 times a week at a time of their preference. For participants who provide consent to the sub-study, the app will also feature the ability to report the results of their test results (upload images of test trips), track testing history, respond to surveys and questionnaires, and access study team's contact information. As an alternative to the app, participants can participate in the study via phone interviews conducted by a centralized study call center. Home test kits will include a QR code for the public health intervention app which will link to DCRI call center/eConsent for those interested in participating. Using scripted interview guides, call center staff will be ready to explain study participation, obtain verbal consent, administer study questionnaires including soliciting test results, and issue phone reminders for participants who chose not to use the study app.

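### Section 9.4.1 plans exact 95% intervals for endpoint proportions and prevalence with no household adjustment, although several members of one household may enrol

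*Combined protocol and SAP*

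**What the plan says.** Section 9.4.1 sets out three things in one paragraph.

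- For endpoint estimates: "Where applicable, exact method confidence intervals will be computed around point estimates". No clustering term is attached. Section 9.4.2 adds only that the intervals are at the 95% level, and Section 9.4.3 asks for 95% confidence around prevalence without naming a variance method.
- For distancing adherence after a positive versus a negative result, the proportions "will be compared using tests of proportion clustered by participants with various levels of intra-participant correlation". The household is not mentioned here.
- For associations between positive results and behavioural measures, exploratory mixed models account for participant and "household correlations".

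On who can enter, Section 4.1 says: "As part of the public health intervention, households will receive test kits". Section 5.1 requires residence in the community, consent and "Age > 8 years at enrollment". Section 5.2 says: "There are no exclusion criteria for this study, if all above inclusion criteria are met". Nothing restricts enrolment to one person per household, and Section 10.1.7 describes the study as direct-to-family.

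Section 9.1 frames the work: "The proposed analysis is primarily descriptive rather than inferential". Section 9 also states: "Additional details of the planned statistical analyses will be provided in a separate statistical analysis plan". That plan is not part of the document supplied.

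**The concern.** In a descriptive study, point estimates and their intervals are the main product. An exact binomial interval is exact only for independent observations. Members of one household share exposure, rules and habits, so infection status and distancing behaviour may well correlate within it. The plan accepts this in its mixed models. Those models estimate associations with a positive result, however, and do not correct an interval around a single proportion.

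At stake is whether a reported 95% interval for adherence, knowledge or prevalence covers at 95%. For a given household size and ICC, the loss of coverage does not go away with a larger sample, because the design effect does not depend on the number of participants.

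**Working it through.** **1. The plan's own precision figures.** Section 9.2 gives margins for a 50% proportion of 3.09%, 1.37% and 0.96% at N = 1,000, 5,000 and 10,000. The simple formula 1.96·√(p(1−p)/N) gives 3.10%, 1.39% and 0.98%. Multiplying by a finite-population factor √((300,000−N)/(300,000−1)) gives 3.09%, 1.37% and 0.96%, and all 12 table rows then match to two decimals. The factor is my inference from the maximum cohort of 300,000 in Section 1.1; the plan does not state it. Either way, participants are treated as independent and there is no household design effect.

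**2. Inputs that the documents do not give (assumptions).** These are m, the members of a household who are analysed, and ICC, the within-household correlation of the outcome. One outcome per person is assumed.

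**3. Formulas.** DEFF = 1 + (m−1)·ICC. The correct width is the unadjusted width × √DEFF. Actual coverage of an unadjusted 95% interval ≈ 2Φ(1.96/√DEFF) − 1.

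| m | ICC | DEFF | Width factor | Coverage | Margin at N = 1,000, 50% |
|---|---|---|---|---|---|
| 1 | any | 1.00 | 1.00 | 95.0% | 3.10% |
| 1.5 | 0.1 | 1.05 | 1.02 | 94.4% | 3.18% |
| 2 | 0.2 | 1.20 | 1.10 | 92.6% | 3.39% |
| 3 | 0.3 | 1.60 | 1.26 | 87.9% | 3.92% |
| 4 | 0.5 | 2.50 | 1.58 | 78.5% | 4.90% |

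The formula assumes equal household sizes. With unequal sizes, m becomes Σm²/Σm. For example, an average of 1.5 made up half of singles and half of pairs gives (1+4)/(1+2) = 1.67, so DEFF = 1 + 0.67·0.1 = 1.07 and coverage is about 94.2%.

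**4. Per-protocol selection.** Section 9.3 runs all analyses in the per-protocol set. If each enrolled member qualifies independently with probability q, DEFF = 1 + (m−1)·q·ICC.

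| m, ICC | q = 0.5 | q = 0.2 |
|---|---|---|
| 2, 0.2 | 1.10, coverage 93.8% | 1.04, 94.5% |
| 3, 0.3 | 1.30, 91.4% | 1.12, 93.6% |
| 4, 0.5 | 1.75, 86.2% | 1.30, 91.4% |

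If completion runs in households, the result moves back towards the first table.

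**5. Does an exact interval protect?** A beta-binomial simulation used about 5,000 participants, 1% prevalence and 8,000 runs. The unadjusted Clopper-Pearson interval covered 95.2% (one per household), 93.2% (2, 0.2), 88.3% (3, 0.3) and 79.1% (4, 0.5). An exact interval at the estimated effective sample size covered 95.2%, 95.8%, 95.2% and 96.1%. At about 1,000 participants and 1%, the interval's own conservatism hides mild clustering: the unadjusted values are 97.5%, 95.7%, 92.6% and 84.0%. There the adjusted interval reached only 93.6% at (4, 0.5), which is why a small-sample correction is needed when positives are few.

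**6. Positive versus negative comparison.** A simulation used about 5,000 participants, three survey waves, 5% positive per wave and no true effect. Type I error at a nominal 5%:

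| m | Outcome ICC | Positivity ICC | Clustered by participant | Clustered by household |
|---|---|---|---|---|
| 2 | 0.2 | 0.2 | 5.3% | 4.9% |
| 3 | 0.2 | 0.2 | 5.9% | 5.1% |
| 3 | 0.5 | 0.5 | 10.5% | 5.0% |
| 4 | 0.5 | 0 | 5.0% | 5.1% |

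The effect is small unless both ICCs are large.

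**The case against.** Section 9.4.1 is a general approach, it says the intervals apply where applicable, and detail is deferred to a separate SAP. Variance estimation is ordinary SAP content, and the authors plainly know about household correlation. This stands to the extent that an unadjusted analysis is not certain. It does not supply the missing adjustment: the only interval method stated assumes independence.

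The size is also uncertain. Each member must opt in and consent, so the average may be close to one. Per-protocol status demands four weeks of testing three times a week plus the surveys, which thins households further. Most endpoints are also reported by demographic stratum, and age or sex strata tend to split households: an opposite-sex pair puts one person in each sex stratum. In absolute terms the missing width is modest. At (2, 0.2) and 50%, the margin goes from 0.98 to 1.07 points at N = 10,000, and from 0.18 to 0.20 at 300,000. All of this stands, and it limits the weight of the point.

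A reader might go further and infer that the positive-versus-negative comparison is invalid because it is clustered by participant only. The documents do not support that. Household-level mixed models of a closely related association are already planned, the hypothesis is exploratory, and the simulated error stays at 5.0% to 5.9% except when both ICCs are 0.5.

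**Conclusion.** The point holds for the intervals around single proportions and prevalence. The stated method has no household term, the enrolment rules allow several members per household, and the plan recognises the correlation elsewhere in the same paragraph. If several members are analysed and their outcomes correlate, the intervals are too narrow. Coverage is about 94.4% to 87.9% over the range from (1.5, 0.1) to (3, 0.3), nearer 95% after per-protocol selection or within age or sex strata, and unchanged with one analysed member per household.

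Three stronger readings are not supported. Coverage near 79% needs four members, all enrolled and analysed, with ICC 0.5, and nothing in the documents points to that. The plan does not ignore household correlation altogether. The Section 9.2 margins are illustrations under independence, not targets that the study would miss.

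This should be changed, but it does not threaten the study. Confidence is medium, because household enrolment, the ICC and the separate SAP are all unknown.

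**What to change.** In Section 9.4.1 and the SAP:

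- Compute intervals for single proportions and prevalence with household-cluster-robust variance, or as exact intervals at the effective sample size n/DEFF with DEFF estimated from that variance. Use a small-sample correction when few households have a positive result.
- Report the number analysed per household in each analysis population, and the estimated ICC.
- Note in Section 9.2 that the margins assume independent participants.
- As a minor consistency step, make household the top-level cluster in the positive-versus-negative comparison, as the planned mixed models already do. Little change is expected at modest ICCs.

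The cost is wording, modest programming in SAS or R, and slightly wider intervals. A coded household identifier is needed. The mixed models already require one, but the schedule in Section 1.3 does not list it and Section 10.1.3 keeps contact and identifying data out of the analysis file. A coded link might be derived from the baseline contact information; if not, a small addition to data collection is needed. If clustering proves absent, the adjusted intervals will barely differ from the planned ones.
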